#### **5.3.5.5 Abnormal Vital Sign Values**

Not every vital sign abnormality qualifies as an AE. A vital sign result should be reported as an AE if it meets any of the following criteria:

- Accompanied by clinical symptoms
- Results in a change in study drug (e.g., dosage modification, treatment interruption, or treatment discontinuation)
- Results in a medical intervention or a change in concomitant therapy
- Clinically significant in the Investigator's judgment

It is the Investigator's responsibility to review all vital sign findings. Medical and scientific judgment should be exercised in deciding whether an isolated vital sign abnormality should be classified as an AE.

If a clinically significant vital sign abnormality is a sign of a disease or syndrome (e.g., high blood pressure), only the diagnosis (i.e., hypertension) should be recorded on the Adverse Event page of the eCRF.

Observations of the same clinically significant vital sign abnormality from visit to visit should not be repeatedly recorded on the Adverse Event page of the eCRF, unless the etiology or severity changes. The initial severity of the event should be recorded, and the severity or seriousness should be updated any time the event worsens or improves.

#### **5.3.5.6 Abnormal Liver Function Tests**

The finding of an elevated ALT or AST (>3x ULN) in combination with either an elevated total bilirubin (>2x ULN) or clinical jaundice in the absence of cholestasis or other causes of hyperbilirubinemia is considered to be an indicator of severe liver injury. Therefore, Investigators must report as an AE the occurrence of either of the following:

- ALT or AST >3 × ULN in combination with total bilirubin >2 × ULN
- ALT or AST >3 × ULN in combination with clinical jaundice

Any other reason than study drug-induced liver injury should be checked, such as viral hepatitis A, B, or C, preexisting or acute liver disease, or another drug capable of causing the observed injury in case these have any clinical probability. The most appropriate diagnosis or (if a diagnosis cannot be established) the abnormal laboratory values should be recorded on the Adverse Event page of the eCRF (see Section 5.3.5.1) either as an SAE or a non-serious AESI (see Section 5.4.2) and must be reported to the Sponsor within 24 hours after learning of the event,

#### **5.3.5.7 Deaths**

All deaths that occur during the protocol-specified AE reporting period (see Section 5.3.1), regardless of relationship to study drug, must be recorded on the Adverse Event page of the eCRF and immediately reported to the Sponsor (see Section 5.4.2). This includes death attributed to progression of NMO.

Death should be considered an outcome and not a distinct event. The event or condition that caused or contributed to the fatal outcome should be recorded as the single medical concept on the Adverse Event page of the eCRF. Generally, only one such event should be reported. The term “**sudden death**” should only be used for the occurrence of an abrupt and unexpected death due to e.g., presumed cardiac causes in a patient with or without preexisting heart disease, within 1 hour of the onset of acute symptoms or, in the case of an unwitnessed death, within 24 hours after the patient was last seen alive and stable. If the cause of death is unknown and cannot be ascertained at the time of reporting, “**unexplained death**” should be recorded on the Adverse Event page of the eCRF. If the cause of death later becomes available (e.g.,

after autopsy), “unexplained death” should be replaced by the established cause of death.

If the death is attributed to progression of NMO “NMO progression” should be recorded on the Adverse Event page of the eCRF.

#### **5.3.5.8 Preexisting Medical Conditions**

A preexisting medical condition is one that is present prior to baseline. Such conditions should be recorded on the General Medical History and Baseline Conditions eCRF.

A preexisting medical condition should be recorded as an AE only if the frequency, severity, or character of the condition worsens during the study. When recording such events on the Adverse Event page of the eCRF, it is important to convey the concept that the preexisting condition has changed by including applicable descriptors (e.g., “more frequent headaches”).

#### **5.3.5.9 Lack of Efficacy or Worsening of NMO**

Events that are clearly consistent with the expected pattern of progression of the underlying disease should not be recorded as AEs. These data will be captured as elements of the efficacy assessment data only. In most cases, the expected pattern of progression will be based on relapse related clinical data. In rare cases, the determination of clinical progression will be based on symptomatic deterioration. However, every effort should be made to document progression using objective criteria. If there is any uncertainty as to whether an event is due to disease progression, it should be reported as an AE.

#### **5.3.5.10 Hospitalization or Prolonged Hospitalization**

Any AE that results in hospitalization or prolonged hospitalization should be documented and reported as an SAE (per the definition of SAE in Section 5.2.2), except as outlined below.

The following hospitalization scenarios are not considered to be SAEs:

- Hospitalization because of NMO relapse
- Hospitalization for respite care
- Planned hospitalization required by the protocol (e.g., for study drug administration)
- Hospitalization for a preexisting condition, provided that all of the following criteria are met:

- The hospitalization was planned prior to the study or was scheduled during the study when elective surgery became necessary because of the expected normal progression of the disease
- The patient has not suffered an AE.

#### **5.3.5.11 Overdoses**

Study drug overdose is the accidental or intentional use of the drug in an amount higher than the dose being studied. An overdose or incorrect administration of study drug is not an AE unless it results in untoward medical effects.

Any study drug overdose or incorrect administration of study drug should be noted on the Study Drug Administration eCRF.

All AEs associated with an overdose or incorrect administration of study drug should be recorded on the Adverse Event page of the eCRF. If the associated AE fulfills serious criteria, the event should be reported as a SAE to the Sponsor within 24 hours after learning of the event (see Section 5.4.2).

### **5.4 IMMEDIATE REPORTING REQUIREMENTS FROM INVESTIGATOR TO SPONSOR**

The Investigator must report the following events to the Sponsor within 24 hours after learning of the event, regardless of relationship to study drug:

- SAEs
- Non-serious AESI
- Pregnancies

The Investigator must report new significant follow-up information for these events to the Sponsor within 24 hours after becoming aware of the information. New significant information includes the following:

- New signs or symptoms or a change in the diagnosis
- Significant new diagnostic test results
- Change in causality based on new information
- Change in the event's outcome, including recovery
- Additional narrative information on the clinical course of the event

Investigators must also comply with local requirements for SAE reporting to the local health authority and IRB/IEC.

#### **5.4.1            Emergency Medical Contacts**

The contact details for the Emergency Medical Contacts will be provided in the Study Manual and the Investigator (Site) File. Medical Monitor names, contact information, and country-specific phone numbers will be included.

#### **5.4.2            Reporting Requirements for Serious Adverse Events and Non-serious Adverse Events of Special Interest**

For reports of SAEs and non-serious AESI, investigators should record all case details that can be gathered within 24 hours on the paper SAE form and fax the completed SAE form to PAREXEL International Pharmacovigilance. Investigators should refer to the Study Manual and the Investigator (Site) File for the current contact information (fax and telephone numbers, and email addresses) for SAE and non-serious AESI reporting.

In the event of fax transmission failure of the SAE form, the site could alternatively e-mail the SAE form to PAREXEL International Pharmacovigilance using the e-mail address provided.

Concurrently the Adverse Event eCRF should be completed immediately (see Section 5.3.1).

#### **5.4.3            Reporting Requirements for Pregnancies**

##### **5.4.3.1        Pregnancies in Female Patients**

Female patients of childbearing potential will be instructed to immediately inform the Investigator if they become pregnant during the study or within 3 months after the last dose of study drug. A paper pregnancy report form should be completed within 24 hours and submitted via fax to PAREXEL International Pharmacovigilance, using the fax numbers provided (see Section 5.4.2). Pregnancy should not be recorded on the Adverse Event page of the eCRF. The Investigator should discontinue study drug and counsel the patient, discussing the risks of the pregnancy and the possible effects on the fetus. Monitoring of the patient should continue until conclusion of the pregnancy. *Any serious adverse events associated with the pregnancy (e.g., an event in the fetus, an event in the mother during or after the pregnancy, or a congenital anomaly/birth defect in the child) should be reported on the Adverse Event eCRF. In addition, the Investigator will update the paper pregnancy report form when updated information on the course and outcome of the pregnancy become available.*

In the event of the fax transmission failure of the pregnancy report form, the completed pregnancy report form could alternatively be sent by e-mail to PAREXEL International Pharmacovigilance using the e-mail address provided.

#### **5.4.3.2 Pregnancies in Female Partners of Male Patients**

Male patients will be instructed through the Informed Consent Form to immediately inform the Investigator if their partner becomes pregnant during the study or within 3 months after the last dose of study drug. A paper pregnancy report form should be completed within 24 hours of learning of the pregnancy and submitted via fax to PAREXEL International Pharmacovigilance, using the fax numbers provided (see Section 5.4.2). In the event of the fax transmission failure of the pregnancy report form, the completed pregnancy report form could alternatively be sent by e-mail to PAREXEL International Pharmacovigilance using the e-mail address provided.

Attempts should be made to collect and report details of the course and outcome of any pregnancy in the partner of a male patient exposed to study drug. The pregnant partner will need to sign an Authorization for Use and Disclosure of Pregnancy Health Information to allow for follow-up on her pregnancy. Once the authorization has been signed, the Investigator will update the paper pregnancy report form *when updated information on the course and outcome of the pregnancy become available*. An Investigator who is contacted by the male patient or his pregnant partner may provide information on the risks of the pregnancy and the possible effects on the fetus, to support an informed decision in cooperation with the treating physician and/or obstetrician.

#### **5.4.3.3 Abortions**

Any spontaneous abortion should be classified as an SAE (as the Sponsor considers spontaneous abortions to be medically significant events), recorded on the Adverse Event page of the eCRF, and reported to the Sponsor within 24 hours after learning of the event (see Section 5.4.2).

#### **5.4.3.4 Congenital Anomalies/Birth Defects**

Any congenital anomaly/birth defect in a child born to a female patient or female partner of a male patient exposed to study drug patient should be classified as an SAE, recorded both on the Adverse Event page of the eCRF and on the paper form, and reported to the Sponsor by faxing within 24 hours after learning of the event (see Section 5.4.2).

#### **5.4.4 Reporting Requirements for Medical Device Complaints**

In this study, PFS with NSD is considered a medical device. The Investigator must report all medical device complaints to the Sponsor or its designee. The Investigator should document as much information as possible on the IMP Deviation Form, including the product batch number, and forward the form to the Sponsor or its designee.

If the medical device results in an AE to the study patient, the event must be recorded on the eCRF (see Section 5.3.5). If the event is serious, SAE form must be completed immediately (i.e., no more than 24 hours after learning of the event), as outlined in Section 5.4.2. If the medical device results in an AE to an individual other than the study patient, the AE should be reported as a spontaneous AE to Sponsor Drug Safety via e-mail (see IMP Deviation Form).

### **5.5 FOLLOW-UP OF PATIENTS AFTER ADVERSE EVENTS**

#### **5.5.1 Investigator Follow-Up**

The Investigator should follow each AE until the event has resolved to baseline grade or better, the event is assessed as stable by the Investigator, the patient is lost to follow-up, or the patient withdraws consent. Every effort should be made to follow all SAEs considered to be related to study drug or study-related procedures until a final outcome can be reported.

During the study period, resolution of AEs (with dates) should be documented on the Adverse Event page of the eCRF and in the patient's medical record to facilitate source data verification. If, after follow-up, return to baseline status or stabilization cannot be established, an explanation should be recorded on the Adverse Event page of the eCRF.

All pregnancies reported during the study should be followed until pregnancy outcome. Follow reporting instructions provided in Section 5.4.3.1.

### **5.6 POST-STUDY ADVERSE EVENTS**

At the Last Observation/Withdrawal visit, the Investigator should instruct each patient to report to the Investigator any subsequent AEs that the patient's personal physician believes could be related to prior study drug treatment or study procedures (e.g., infections or reactivation of previously acquired infective agents).

The Investigator should notify the Sponsor of any death, SAE (e.g., development of cancer) and non-serious AESI of concern occurring at any time after the Withdrawal Visit or Last Observation Visit if the event is believed to be related to prior study drug treatment or study procedures. The Sponsor should also be notified if the Investigator

becomes aware of a congenital anomaly/birth defect in a subsequently conceived offspring of a patient that participated in this study.

The Investigator should report the event via a paper SAE form.

## **5.7 EXPEDITED REPORTING TO HEALTH AUTHORITIES, INVESTIGATORS, INSTITUTIONAL REVIEW BOARDS, AND ETHICS COMMITTEES**

The Sponsor will promptly evaluate all SAEs and AESIs against cumulative product experience to identify and expeditiously communicate possible new safety findings to investigators, IRBs, ECs, and applicable health authorities based on applicable legislation.

To determine reporting requirements for single AE cases, the Sponsor will assess the expectedness of these events *through use of the reference safety information in the satralizumab Investigator's Brochure*.

The Sponsor will compare the severity of each event and the cumulative event frequency reported for the study with the severity and frequency reported in the applicable reference document.

Reporting requirements will also be based on the Investigator's assessment of causality and seriousness, with allowance for upgrading by the Sponsor as needed.

Expedited reporting to Health Authorities will follow each country's specific regulations.

An IDMC will periodically monitor the incidence of AEs (not only expedited reporting to Health Authorities but also all AEs) during the *double-blind period of the study*. An aggregate report of any clinically relevant imbalances that do not favor the test product will be submitted to health authorities.

## **6. STATISTICAL CONSIDERATIONS AND ANALYSIS PLAN**

This section outlines the statistical analysis strategy and procedures for the study. A detailed methodology for statistical analyses of the data collected in this trial will be documented in a Statistical Analysis Plan (SAP).

### **6.1 ANALYSIS POPULATIONS**

#### **6.1.1 Efficacy Analysis Populations**

The intent-to-treat (ITT) population will serve as the primary population for the analysis of efficacy, which consists of all randomized patients in the double-blind

period in the study. Patients will be analyzed as randomized for analysis purposes in the ITT.

The Per-Protocol Set (PPS) will include all patients in the ITT population who received at least 3 doses of study drug, and without any major protocol deviations which are considered to have an impact on efficacy. Patients will be analyzed as treated for analysis purposes in the PPS.

### **6.1.2 All-Patients-Treated Population**

The All-Patients-Treated (All satralizumab) population will be defined as all enrolled patients who took at least one dose of active study drug at any time.

### **6.1.3 Safety Analysis Populations**

All safety variables will be analyzed based on the Safety Population (SAF). The SAF population will include all randomized patients who have received at least one dose of study drug. Patients will be analyzed as treated for analysis purposes in the SAF.

### **6.1.4 Pharmacokinetics Per-Protocol Set and Pharmacodynamics Analysis Population**

The Pharmacokinetics Per-Protocol Set (PK-PPS) and immunogenicity (ADA) will include all patients in the SAF with at least 1 valid post-dose concentration result with a dosing record and sampling time. Pharmacodynamics variables (IL-6, sIL-6R, hsCRP, anti-AQP4Ab, plasmablast) will be analyzed using the SAF population.

### **6.1.5 Analysis population for adolescents**

The adolescent population will be defined as all adolescent patients who have received at least one dose of study drug.

## **6.2 DETERMINATION OF SAMPLE SIZE**

Approximately 70 patients need to be recruited and randomized in a 1:1 ratio to the two treatment groups (satralizumab and placebo). The sample size considerations are based on the following assumptions:

1. A two-sided log-rank test
2. 80% power at the 5% significance level
3. A 66.5% reduction in the risk of relapse, i.e., the TFR hazard ratio of satralizumab over placebo is 0.335
4. TFR in the placebo arm following an exponential distribution, with hazard rate  $h(t)=0.4184$
5. A 2-year dropout rate of 10%

Based on these assumptions, 26 TFR events are needed for the primary analysis. TFR events are defined as protocol-defined relapses confirmed by the CEC with EDSS/FSS assessment performed by the examining assessor within 7 days after relapse symptoms were reported to site by the patient. The maximum accrual rate is estimated to be approximately 8 patients per month, after the first patient in (FPI) plus 8 months of ramp up. The 70 patients enrolled over one year and followed for an additional one and a half years will provide 26 TFR events. The primary analysis will be performed once 26 TFR events have been observed. The Sponsor will conduct a blind review of the data including accumulation of events during the double-blind period and may take appropriate action such as to increase the number of patients or to extend the double-blind period based on this blind review.

It has been assumed that the number of relapses will follow a Gamma-Poisson distribution and that the variance/mean ratio will be a constant value of  $\sqrt{2}$ . This distribution was assumed and the ratio was estimated using data from MS trials (Gold et al. 2012; Kappos et al. 2010) because there are no approved medications for NMO and no raw data from patients with this indication are available.

Because the mean ARR of NMO patients is estimated at 0.753 (Cossburn et al. 2012) and patients entering this study have an ARR  $\geq 1$  owing to inclusion criterion 2, we calculate the zero-truncated mean of the Gamma-Poisson distribution with the mean of 0.75 and the mean and variance ratio of  $\sqrt{2}$ , then the baseline ARR is estimated at 1.6. The two Phase 3 MS trials above reported that pre- and post-baseline ARR in the placebo group were 1.4 and 0.4, so the post-baseline ARR in placebo group in this trial is estimated at 0.5.

Using the proportion of zero under supposed ARR distribution, we estimate the relapse-free rate at a year in placebo group at 65.8%. The relapse-free rate is assumed to follow the exponential distribution with a constant hazard, and then we set the hazard ratio of 0.4184 in placebo group.

According to tocilizumab case reports in NMO patients, the pre- and post- baseline relapse counts were reduced from total 4 counts per 6 months to 1 count per 6 months. Then the pre- and post- baseline ratio of 0.25 is used as the estimation of the mean ARR ratio of tocilizumab compared with placebo. Moreover, the azathioprine's data showed the pre- and post- baseline mean ARR ratio was 0.33 ( $=0.77/2.32$ , the mean ARR were estimated from the median ARR and the distribution supposition above) and the rituximab data showed the pre- and post-baseline mean ARR ratio was 0.125 ( $=0.3/2.4$ ), then we estimate the rituximab mean ARR ratio compared with azathioprine at 0.38 ( $=0.125/0.33$ ).

Under the assumption of ARR and relapse-free rate distribution above, the mean ARR ratio is coincided with the hazard ratio. Tocilizumab hazard ratio data (0.25) could have a possibility of overestimation because of the case report with only three patients and the hazard ratio between rituximab and azathioprine (0.38) is the comparison with an active control, then we consider the satralizumab hazard ratio compared to placebo should exist between 0.25 and 0.38. So we have set the satralizumab hazard ratio compared with placebo at 0.335.

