#### **Determination of Sample Size**

The sample size considerations are based on the following assumptions: (1) a two-sided log-rank test; (2) 80% power at the 5% significance level; (3) a 66.5% reduction in the risk of relapse, i.e., the TFR hazard ratio of satralizumab over placebo is 0.335; (4) TFR in the placebo arm following an exponential distribution, with hazard rate  $(h(t))=0.4184$ ; (5) a 2-year dropout rate of 10%.

Based on these assumptions, 26 CEC-confirmed TFR events are needed for the primary analysis. The maximum accrual rate will be approximately 8 patients per month, after the FPI plus 8 months of ramp up. The 70 patients enrolled over 1 year and followed for an additional one and a half years will provide 26 TFR events.

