#### **6.5.1 Primary Efficacy Endpoint**

The primary efficacy endpoint is TFR based on protocol-defined relapses confirmed by the CEC with EDSS/FSS assessment performed by the examining assessor within 7 days after relapse symptoms were reported to site by the patient. TFR is defined as the time from the date of the randomization until the first occurrence of relapse throughout the double-blind period. The time point of relapse onset is defined as the time at which the patient experiences any new or worsening neurological NMO representing clinical relapse(s). Events which are judged by the CEC to meet the protocol-defined relapse will be included in the primary analysis of the primary endpoint if EDSS/FSS is assessed by the examining assessor within seven days after

the patient reports the symptoms to the site. For patients who have not relapsed, not switched baseline treatment or not increased baseline treatment at the time of analysis, the TFR will be censored on the date when total number of protocol-defined relapses judged by CEC reaches 26. For patients who have switched baseline treatment or increased baseline treatment, the TFR will be censored on the date of switching or increasing the baseline treatment. For patients who have received rescue therapy without experiencing a protocol-defined relapse for which the EDSS/FSS assessment was not performed within seven days after the patient reports the symptoms to the site, the TFR will be censored on the date of receiving rescue therapy.

The primary analysis of the study is to test the equality of the TFR distribution in the satralizumab (SA237) +baseline treatment (satralizumab [SA237]) and Placebo +baseline treatment (placebo) arms:

$$H_0: TFR_{SA237} = TFR_{\text{placebo}} \text{ versus } H_1: TFR_{SA237} \neq TFR_{\text{placebo}}$$

A stratified two-sided log-rank test using strata of baseline ARR (one vs. more than one) and geographical region will be used.

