5.10.2 Primary Efficacy Variable

The primary efficacy analyses will be based on the ITT population. Supportive evaluations will be performed using the PPS population.

The primary efficacy endpoint is TFR based on protocol-defined relapses confirmed by the CEC with EDSS/FSS assessment performed by the examining assessor within 7 days after relapse symptoms were reported to site by the subject. TFR is defined as the time from the date of the randomization until the first occurrence of relapse throughout the study. Time point of relapse onset is defined as time at which the subject experiences any new or worsening neurological NMO representing clinical relapse(s) which is later confirmed by the CEC as protocol-defined.

Censor is defined as the earliest day of 1) the end of double blind period for efficacy analysis, 2) switching or increasing the baseline treatment (for details on the identification of the switch and increase in baseline therapy see appendix 7.4), or 3) receiving rescue therapy for clinical relapse.

The primary analysis of the study is to test the equality of the TFR distribution based on protocol-defined relapse in the SA237 + baseline treatment (SA237) and Placebo + baseline treatment (placebo) arms:

$$H_0: TFR_{SA237} = TFR_{\text{placebo}} \text{ versus } H_1: TFR_{SA237} \neq TFR_{\text{placebo}}$$

A stratified two-sided log-rank test using strata of baseline ARR (one vs. more than one) and geographical region (Asia and EU/Other) will be used.

The Kaplan-Meier method will be used to estimate the TFR based on protocol-defined relapses distribution for each treatment group. The Kaplan-Meier curve will provide a visual description of the differences across treatment groups. In addition, estimates of the treatment effect will be expressed as hazard ratio and 95% CIs using a stratified (baseline ARR and geographical region) Cox proportional-hazards model (Exact method will be used for tie data). Treatment by covariate interactions will be assessed by including the pairwise interaction terms in the Cox proportional-hazards model.

The following summary tables, figures and analysis will be provided for the ITT and PPS:

- A summary table of Kaplan-Meier estimate of TFR (protocol-defined relapse) will be presented by treatment group.
- A figure of Kaplan-Meier estimate of TFR (protocol-defined relapse) will be presented by treatment group.
- Analysis of TFR (protocol-defined relapse) will be performed using the stratified log-rank test.

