5.14 Determination of Sample Size

Approximately 70 subjects need to be recruited and randomized in a 1:1 ratio to the two treatment groups (SA237 and placebo). The sample size considerations are based on the following assumptions:

- A two-sided log-rank test
- 80% power at the 5% significance level
- A 66.5% reduction in the risk of relapse, i.e. the TFR hazard ratio of SA237 over placebo is 0.335
- TFR in the placebo arm following an exponential distribution, with hazard rate for one year $h(t) = 0.4184$
- A 2-year dropout rate of 10%

Based on the assumptions, 26 TFR events are needed for the primary analysis. TFR events are defined as protocol-defined relapses confirmed by the CEC with EDSS/FSS assessment performed by the examining assessor within 7 days after relapse symptoms were reported to site by the subject. The maximum accrual rate is estimated to be approximately 8 subjects per month, after the FPI plus 8 months of ramp up. The 70 subjects enrolled over one year and followed for an additional one and a half year will provide 26 TFR events. The primary analysis will be performed once 26 TFR events have been observed. Sponsor will conduct blind review during the double-blind period and might take appropriate action based on blind review.

Since the annualized relapse rate (ARR) is the number of relapse counts observed when every subject is observed for a year and suppose that the distribution follows a Gamma-Poisson distribution and that the mean and variance ratio (variance / mean) is a constant value of $\sqrt{2}$. The ratio was estimated using MS trials' data^{1,2)} because there are no approved medications for NMO.

Because the mean ARR of NMO subjects is estimated at 0.753³⁾ and eligibility criterion 2 says more than one ARR subjects are selected, we calculate the zero-truncated mean of the Gamma-Poisson distribution with the mean of 0.75 and the mean and variance ratio of $\sqrt{2}$, then the baseline ARR is estimated at 1.6. The two phase III MS trials above reported that pre- and post- baseline ARR in the placebo group were 1.4 and 0.4, so the post-baseline ARR in placebo group in this trial is estimated at 0.5.

Using the proportion of zero under supposed ARR distribution, we estimate the relapse-free rate at a year in placebo group at 65.8%. The relapse-free rate is assumed to follow the exponential distribution with a constant hazard, and then we set the hazard for one year of 0.4184 in placebo group.

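### Stated 80% power at 26 events is a large-sample figure; simulating the listed assumptions gives about 77%

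*Protocol*

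**What the plan says.** Protocol 6.2 lists five planning assumptions. The test is "A two-sided log-rank test", the operating characteristics are "80% power at the 5% significance level", the hazard ratio is 0.335, the placebo hazard is 0.4184 per year (exponential), and dropout is 10% over two years. It then states: "Based on these assumptions, 26 TFR events are needed for the primary analysis". It ties the primary analysis to the 26th event and plans 70 patients randomized 1:1.

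The synopsis repeats the pairing, "a two-sided log-rank test; (2) 80% power at the 5% significance level", and concludes: "Based on these assumptions, 26 CEC-confirmed TFR events are needed for the primary analysis". SAP 5.14 has the same list and the same conclusion: "Based on the assumptions, 26 TFR events are needed for the primary analysis". None of the three places names the formula used.

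The primary analysis is described more fully elsewhere. Protocol 6.5.1 says "A stratified two-sided log-rank test using strata of baseline ARR (one vs. more than one) and geographical region will be used", and SAP 5.10.2 says "A stratified two-sided log-rank test using strata of baseline ARR (one vs. more than one) and geographical region (Asia and EU/Other) will be used". Two factors with two levels each make four strata. The sample-size lists do not mention stratification.

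**The concern.** The usual formula that links events to power for a log-rank test is a large-sample approximation, and it works best when the hazard ratio is not far from 1. Here there are only 26 events and the assumed hazard ratio is 0.335. In that setting the formula can promise more power than the test delivers. A reader of the three sections would take 80% as the chance of detecting the assumed effect at the planned analysis. If the true figure is lower, the risk of missing that effect on the primary endpoint is understated. The planned test is also stratified, with 26 events spread over four strata, which raises the question whether the listed power applies to it at all.

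**Working it through.** **Inputs from the documents (Protocol 6.2, SAP 5.14).** 70 patients, 1:1; placebo hazard 0.4184 per year; hazard ratio 0.335, so the satralizumab hazard is 0.335 × 0.4184 = 0.1402; two-year dropout 10%; two-sided 5%; analysis at the 26th event; accrual over one year.

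**Assumed, because not given.** Exponential dropout equal in both arms, with rate −ln(0.9)/2 = 0.0527 per year. Uniform accrual, or a linear 8-month ramp to 8 patients per month. For the stratified test only: block size, stratum shares and stratum hazards.

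**Step 1: reproduce the plan's figure.** The Schoenfeld formula for 1:1 allocation is

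d = 4 × (1.960 + 0.8416)² / (ln 0.335)² = 4 × 7.849 / 1.196 = 26.25.

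Power at 26 events = Φ(√26/2 × 1.0936 − 1.960) = Φ(0.828) = 79.6%.

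So 26 events and 80% are reproduced to rounding. The Freedman formula gives 31.6 events and does not match, so Schoenfeld is the likely source, although the documents do not say so.

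**Step 2: simulate the listed assumptions, log-rank test without strata, cut at the 26th event.** 60,000 trials each, Monte Carlo standard error about 0.2 points:

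- permuted blocks of 4: 76.7%
- fixed 35/35: 76.7%
- ramped accrual: 77.0%

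Separately coded simulations gave 76.3% to 77.2%. A small check with a library log-rank routine (4,000 trials, standard error 0.7 points) gave 77.8%. Taking 76.7%, the gap to the formula is 79.6 − 76.7 = 2.9 points.

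**Step 3: the planned stratified test, with assumed strata.** Randomization was in blocks within strata, since Protocol 4.2 stratifies it by the same two factors.

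| Scenario | Stratified | Unstratified, same data |
|---|---|---|
| Four equal strata, equal hazards | 75.2% | 76.7% |
| Placebo hazard 2 times higher in the ARR >1 strata | 75.3% | 75.1% |
| Placebo hazard 4 times higher in the ARR >1 strata | 75.8% | 70.5% |

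With equal hazards, four stratum splits and three block sizes gave 74.6% to 75.5% stratified; a smaller separate run (15,000 trials) gave 74.3%. With equal hazards, stratifying costs about 76.7 − 75.2 = 1.5 points. With a twofold difference the two tests are level, and with a fourfold difference the stratified test is clearly better. The unequal-hazard runs depart from the listed exponential assumption, because a mixture of exponentials is not exponential.

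**Step 4: type I error.** 4.9% unstratified and 5.1% stratified (50,000 trials).

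**Step 5: scale.** Over the plan's own hazard ratio range, simulated power without strata is 91.7% at 0.25 and 66.4% at 0.38.

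**The case against.** The strongest reply is that nothing has been miscalculated. The plan lists 80% as a design target, the standard formula meets it to rounding, and choosing simulation over that formula is a choice of method. This stands in part: a reader might infer an arithmetic error in the 26 events, and the documents do not support that.

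The gap is also small beside the uncertainty in the inputs. On the same formula, 77% power at 26 events corresponds to a hazard ratio of about 0.347 instead of 0.335, and Protocol 6.2 openly sets 0.335 by judgement between 0.25 and 0.38. That limits the importance of the point, but it does not make 80% the power under the listed assumptions.

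A second inference would be that the planned stratified test has 75% power, or that stratifying is what costs power. The documents do not support either as a firm claim. They give no stratum shares, block size or stratum hazards, and the loss from stratifying disappears once the strata differ in hazard. Nor do the lists call the planning test unstratified; they leave the matter open, and the synopsis names the stratified test just before its sample-size paragraph.

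Finally, a cut at 2.5 years instead of at 26 events would give about 27 events and 78.3% to 78.6% power without strata. That is closer to 80% but still below it, and the plan ties the analysis to 26 events. The blinded review allowed in Protocol 6.2 and the completed double-blind period (Protocol 1.3) bear on how much the point matters, not on whether the figure is right.

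**Conclusion.** The point holds as a minor one about the reported power. Under the listed assumptions, with the analysis at the 26th event, a two-sided log-rank test has about 77% power and not 80%. The chance of missing the assumed effect is therefore about 23% instead of 20%. This rests only on the documents' own inputs plus the accrual and dropout shapes stated above; the accrual and allocation variants moved the result by about 0.3 points.

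The figure of about 75% for the stratified test is secondary and conditional on assumed strata.

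A reader might go further and conclude that the trial is invalid or that the event target has to be raised. Neither follows. The test holds its type I error. For scale, about 28 events would bring the simulated unstratified power to 80%, a difference of two events, which is small beside the uncertainty in the hazard ratio.

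**What to change.** In Protocol 6.2, the synopsis and SAP 5.14, restate the power in one sentence, for example: *With 26 events and a hazard ratio of 0.335, power is about 77% by simulation under the listed assumptions (about 80% by the large-sample approximation); the stratified primary test may be slightly lower, about 75% under assumed strata.* The sponsor should confirm which approximation was used before it is named.

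Leave the event target, the test and the number of patients unchanged. The cost is one sentence in three places and a slightly less favourable stated figure.
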